| BMI | body mass index |
| bpm | beats per minute |
| CF | cystic fibrosis |
| CFTR | cystic fibrosis transmembrane conductance regulator |
| CRF | case report form |
| ECG | electrocardiogram |
| eCRF | electronic case report form |
|  |  |
| F508del | CFTR gene mutation with an in-frame deletion of a phenylalanine codon corresponding to position 508 of the wild-type protein |
| IDMC | independent data monitoring committee |
| IVA | ivacaftor |
| LCI | lung clearance index |
| LFT | liver function test |
| LLN | lower limit of normal |
| max | maximum value |
| MedDRA | Medical Dictionary for Regulatory Activities |
| min | minimum value |
| N | number of subjects |
| PBO | placebo |
|  |  |
| PT | preferred term |
| q12h | every 12 hours |
| QRS | Q, R, and S-wave define the QRS-complex in an ECG |
| QT | QT interval: The duration of ventricular depolarization and subsequent repolarization; it is measured from the beginning of the QRS complex to the end of the T wave |
| QTcF | QT interval corrected for heart rate with Fridericia's correction |
| SAE | serious adverse event |
| SAP | Statistical Analysis Plan |
| SD | standard deviation |
| SOC | system organ class |
| TEAE | treatment-emergent adverse event |
| TEZ | tezacaftor |
| ULN | upper limit of normal |
| WHODD | World Health Organization Drug Dictionary Enhanced |

4 INTRODUCTION

Study VX17-661-116 (Study 116) is a Phase 3, Open-label, rollover study to evaluate the safety and efficacy of long-term treatment with tezacaftor in combination with ivacaftor (TEZ/IVA) in subjects with cystic fibrosis (CF) aged 6 years and older, homozygous or heterozygous for the *F508del-CFTR* mutation.

Study 116 Part A evaluates safety and efficacy of treatment with TEZ/IVA over 96 weeks in subjects aged 6 years and older who were enrolled in parent Study VX15-661-113 Part B (Study 113B) or Study VX16-661-115 (Study 115).

This statistical analysis plan (SAP) is for the final analysis of Study 116 Part A which is based on an approved clinical study protocol (CSP) (Version 2.0, dated 08 November 2019), as well as the most recent approved electronic case report form (eCRF), and the most recent approved eCRF completion guidelines.

This SAP (Methods) documents the statistical analyses and data presentation of the safety and efficacy endpoints during Study 116 Part A for subjects who previously participated in Study 113 Part B or Study 115 and subsequently enrolled in Study 116 Part A.

Due to the outbreak of COVID-19 during Study 116 Part A, to ensure continued safety of subjects who *cannot* travel to the study sites for their visits (for any reason due to COVID 19); specific alternative measures are being implemented to minimize the risk of exposure to COVID 19 (COVID-19 Clinical Study Protocol Addendum for Cystic Fibrosis [Version 2.0, dated 15 May 2020]). This SAP summarizes the additional statistical analyses that are related to these alternative measures.

The Vertex Biometrics Department or designee will perform the statistical analysis described in this document; SAS (Version 9.4 or higher) will be used to generate all statistical outputs (tables, figures, listings, and datasets). This SAP will be finalized and approved prior to the database lock of Study 116 Part A.

Any revisions to the approved SAP will be documented and approved in an amendment to the SAP.

5 STUDY OBJECTIVES

5.1 Primary Objective

To evaluate the long-term safety and tolerability of TEZ/IVA in subjects with CF aged 6 years and older, who are homozygous or heterozygous for *F508del* in Part A.

5.2 Secondary Objective

To evaluate the long-term efficacy of TEZ/IVA in subjects with CF aged 6 years and older, who are homozygous or heterozygous for *F508del* in Part A.

6 STUDY ENDPOINTS

6.1 Primary Endpoint

Safety and tolerability of long-term TEZ/IVA treatment in Study 116 Part A will be evaluated based on adverse events (AEs), clinical laboratory values (serum chemistry, hematology, lipids, and vitamins), standard 12-lead ECGs, physical examinations (PEs), vital signs, ophthalmologic examinations, and pulse oximetry.

6.2 Secondary Endpoints

As secondary endpoints, the following efficacy endpoints will be analyzed:

[figure not shown]
- Absolute change from baseline in lung clearance index_{2.5} (LCI_{2.5}; for subjects from Study 115 and the Study 113 Part B LCI Sub study only)
- Absolute change from baseline in sweat chloride
- Absolute change from baseline in Cystic Fibrosis Questionnaire–Revised (CFQ-R) respiratory domain score
- Absolute change from baseline in body mass index (BMI)

7 STUDY DESIGN

7.1 Overall Design

Study 116 is a Phase 3, multicenter, open-label, 2-part, rollover study in subjects with CF aged 6 years and older, who are homozygous or heterozygous for *F508del* and who completed the Week 24 Visit in Study 113 Part B or the Week 8 Visit in Study 115. A schematic of the study design is shown in Figure 7-1.

Figure 7-1 VX17-661-116 Study Design

Note: Subjects ≥12 years old will receive TEZ 100 mg qd/IVA 150 mg q12h regardless of weight (in Part A and Part B).

IVA: ivacaftor, q12h: every 12 hours, qd: daily, TEZ: tezacaftor

7.2 Sample Size and Power

Study 116 Part A enrolled subjects from Study 113 Part B and Study 115. No formal sample size calculations were performed. Approximately 56 subjects from Study 113 Part B and approximately 65 subjects from Study 115 were potentially eligible for enrollment.

7.3 Randomization

Study 116 Part A is an open-label study with a single treatment arm, and dose is determined by body weight and age. Subjects are not randomized.

7.4 Blinding and Unblinding

Study 116 Part A is an open-label study. Subjects and their parent/caregiver were not informed of their study related LCI, [REDACTED] or sweat chloride results during the study regardless of whether the subject has prematurely discontinued treatment or not.

8 ANALYSIS SETS

The following analysis sets are defined for Study 116 Part A: All Subjects Set, Safety Set, Full Analysis Set, 113B/116 Full Analysis Set, 115/116 Full Analysis Set, and 113B/116 LCI Full Analysis Set.

Enrolled subjects are those who signed a consent/assent form and had an enrollment date in the CRF for Part A.

All Subjects Set

The **All Subjects Set** will be defined as all subjects who were enrolled in Study 116 Part A or received at least 1 dose of TEZ/IVA in Study 116 Part A. This analysis set will be used for all individual subject data listings and the disposition summary table, unless specified otherwise.

Full Analysis Set (FAS)

The **Full Analysis Set (FAS)** will be defined as all subjects who were enrolled in Study 116 Part A, who received at least 1 dose of TEZ/IVA in Study 116 Part A and have an eligible genotype. The FAS will be used for efficacy analyses, unless otherwise specified.

115/116 Full Analysis Set (FAS), 113B/116 FAS and 113B LCI/116 FAS

The 115/116 FAS will be defined as the subset of FAS who were enrolled in parent Study 115. The 113B/116 FAS will be defined as the subset of FAS who were enrolled in parent Study 113B. The 113B/116 LCI FAS will be defined as the subset of Study 113B subjects who participated in the LCI sub-study in Study 113B.

Safety Set

The **Safety Set** will be defined as all subjects who are enrolled in study 116 Part A and who received at least 1 dose of TEZ/IVA in Study 116 Part A. The Safety Set will be used for all safety analyses, unless otherwise specified.

9 ANALYSIS PERIOD

The analysis period used for safety and efficacy endpoints is described below.

9.1 Study 116 Analysis Periods

The Safety analysis period is defined as the **treatment emergent (TE) Period**. The safety analysis period begins at the first dose of study drug in Study 116 Part A and ends 28 days after the last dose of study drug in Study 116 Part A, or at the date of Study 116 Part A participation completion, whichever occurs first.

The safety analyses will be performed on the Safety Set over the Safety Analysis Period, unless otherwise specified.

Safety and tolerability will be assessed by clinical review of all relevant parameters including AEs, Physical Exams, ophthalmologic examinations, clinical laboratory values, vital signs, ECG measurements, and pulse oximetry.

Only descriptive summaries will be presented, and no statistical testing is planned.

Completion of study participation in Study 116 Part A is defined as one of the following:

- For subjects who complete Study 116 Part A and do not roll over to Part B: The Safety Follow-up Visit
- For subjects who complete Study 116 Part A and roll over to Part B or transition to Commercial Drug: The Week 96 Visit
- For subjects who prematurely discontinue study drug treatment but do not withdraw consent in Study 116 Part A: the latest of early treatment termination (ETT) Visit, or Safety Follow-up Visit (if applicable)
- For subjects who withdraw consent in Study 116 Part A: date of withdrawal of consent
- For subjects who are lost to follow-up in Study 116 Part A: the date of last contact

The efficacy analysis period begins at the first dose of study drug in Study 116 Part A and ends at the last study visit at which efficacy data are collected in Study 116 Part A as described in the visit window in the Appendix A. The efficacy analysis will be performed on all subjects in the FAS by parent study for the efficacy analysis period, unless specified otherwise.

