9.1.3 Early Termination of Treatment

If the subject prematurely discontinues study treatment, an ETT Visit should be scheduled as soon as possible after the subject/caregiver decides to terminate study treatment. Subjects who prematurely discontinue treatment will also be required to complete the Safety Follow-up Visit, approximately 28 (\pm 7) days after their last dose of study drug.

If the ETT Visit occurs 3 weeks or later following the last dose of study drug, then the ETT Visit will replace the Safety Follow-up Visit, and a separate Safety Follow-up Visit will not be required.

If a subject chooses to continue onto a commercially available Vertex CFTR modulator (i.e., TEZ/IVA [Symdeko], Kalydeco, Orkambi™, or another approved TEZ/IVA-containing drug), the ETT Visit will be completed before dosing with the commercial drug begins, and the Safety Follow-up Visit (Section 9.1.2) will not be required.

If a subject is continuing onto TEZ/IVA supplied via a Vertex-sponsored managed access program (MAP), the ETT Visit will be completed before dosing with TEZ/IVA via the MAP, and the Safety Follow-up Visit will not be required.

Alternatively, if local health authorities decline to approve, or if clinical benefit is not demonstrated for the use of TEZ/IVA for the treatment of CF in populations enrolled in Study 116, subjects with the relevant *CFTR* genotypes may be discontinued after communication to investigators and IRBs/IECs of the risks/benefits related to the safety and efficacy observed for the subset of subjects concerned. If subjects are discontinued from the study, an ETT Visit should occur within 7 days of the last dose of study drug and a Safety Follow-up Visit should occur within 28 (\pm 7) days after the last dose of study drug.

If the subject/caregiver withdraws consent for the study, no further evaluations should be performed, and no additional data should be collected. Vertex may retain and continue to use any data and samples collected before such withdrawal of consent.

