13.1.1.3 Documentation of Adverse Events

All AEs will be collected from the time ICF is signed until the following time points:

- For subjects who do not enroll: until time of withdrawal of consent
- For enrolled subjects who have a Safety Follow-up Visit: through the Safety Follow-up Visit
- For enrolled subjects who do not have a Safety Follow-up Visit, the **earliest** of
 - o 28 days after the last dose of study drug, or
 - o the ETT Visit, if that visit is 3 weeks or later following the last dose of study drug (see Section 9.1.3)
- For enrolled subjects who do not have a Safety Follow-up Visit because they will transition to commercially available CFTR modulator, or if the subject will receive TEZ/IVA through a Vertex-sponsored MAP: through the ETT Visit (Section 9.1.3)

All subjects/caregivers will be queried, using nonleading questions, about the occurrence of AEs at each study visit. When possible, a constellation of signs and/or symptoms will be identified as 1 overall event or diagnosis. All AEs for enrolled subjects will be recorded in the CRF and source document. For subjects who consent, but do not subsequently enroll in the study, AEs will be recorded only in the subject's source documents. The following data will be documented for each AE:

- Description of the event
- Classification of “serious” or “nonserious”
- Date of first occurrence and date of resolution (if applicable)
- Severity
- Causal relationship to study drug(s)
- Action taken
- Outcome
- Concomitant medication or other treatment given

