
Consenting of Subjects ICFs may be provided electronically or by post mail to subjects (and/or caregivers, as indicated per protocol). The subjects and/or caregivers will review the ICF with an appropriately qualified member of the investigator’s team via telephone contact or video call. After this review, subjects and/or caregivers will consent (or assent, if applicable), and/or re-consent verbally and by signing and dating the ICF and returning it to the site via post mail. The signed and dated ICF will then be signed and dated by the investigator.
 
Subjects participating in select studies may have the opportunity to enroll in longterm extension studies. Informed consent (or assent, if applicable), and/or re-consent for subjects (and/or caregivers, as indicated per protocol) may be obtained per the same process described above, as applicable.
	
To provide alternative methods of obtaining re-consent or consent, as applicable, while ensuring subject safety.
	
[REDACTED]
 
[REDACTED]
 
[REDACTED]
 
VX17-661-116
 
[REDACTED]

Study Drug Shipping Study drug may be shipped directly from the site to the subject, as applicable, and if permitted by local regulations; subject protected health information will not be released to Vertex.
 
Reconciliation, return, and destruction of study drug will continue to occur at the clinical site as indicated per protocol and in adherence to local regulations.
	
To ensure subjects can continue treatment with study drug without interruption while ensuring their safety.
 
To clarify that despite these alternative measures, reconciliation, return, and destruction of study drug will remain as indicated per protocol.
	
[REDACTED]

In-home Visits and/or Telephone Contact Study visits may be conducted as in-home visits by qualified personnel as requested by participating sites on a per-subject basis. In addition, all subjects may be contacted by site personnel by telephone or video call, irrespective of in-home visits.
	
To provide subjects the opportunity to continue participation in the clinical studies while ensuring their safety by minimizing the risk to COVID-19 exposure through travel.
	
[REDACTED]
 
[REDACTED]
 
[REDACTED]

Summary of Changes in Ongoing CF Clinical Studies for Subjects Who Cannot Travel to the Study Site

Protocol Change	Protocol Change	Protocol Change
Addendum Version 1.0, dated 24 April 2020		

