10.3.1 Adverse Events

For analysis purposes, AEs will be classified as pretreatment adverse events (AEs), TEAEs, or post-treatment AEs, defined as follows:

- **Pretreatment AE** any AE that started before the first dose of study drug.
- **TEAE:** any AE that worsened (either in severity or seriousness) or that was newly developed during the TE period.

- **Post-treatment AE:** any AE that worsened (either in severity or seriousness) or that was newly developed after the TE period.

For AEs with completely missing or partially missing start dates, if there is no clear evidence that the AEs started before or after the first dose of study drug during the respective TE period, the AEs will be classified as TEAEs.

Details for imputing missing or partial AE start/end dates are defined in [Appendix E](#).

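### When an early discontinuer has ETT within 3 weeks of the last dose and the required Safety Follow-up Visit does not take place, SAP 9.1 appears to end the treatment-emergent period at ETT, although the protocol collects AEs to day 28

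*SAP*

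**What the plan says.** SAP 9.1 states that the safety analysis period, which is the TE period, "ends 28 days after the last dose of study drug in Study 116 Part A, or at the date of Study 116 Part A participation". The second limit is the date on which participation is complete, and the earlier of the two applies. The section then defines completion by type of subject:

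- Early discontinuer who has not withdrawn consent: "the latest of early treatment termination (ETT) Visit, or Safety Follow-up Visit (if applicable").
- Lost to follow-up: "For subjects who are lost to follow-up in Study 116 Part A: the date of last contact".
- Consent withdrawn: the date of withdrawal.
- Death: no rule of its own.

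Protocol 12.3 leaves the definition of completion to the SAP.

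Protocol 9.1.3 says that "an ETT Visit should be scheduled as soon as possible after the subject/caregiver decides to terminate study treatment". It also requires a Safety Follow-up Visit about 28 (±7) days after the last dose. The protocol drops that visit in two situations: ETT takes place 3 weeks or more after the last dose, or the subject moves to a commercial CFTR modulator or to TEZ/IVA through a managed access program (MAP).

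Protocol 13.1.1.3 sets the end of AE collection. "For enrolled subjects who do not have a Safety Follow-up Visit, the" earlier of two limits applies. One is "28 days after the last dose of study drug, or" and the other is the ETT Visit, which counts only if it is 3 weeks or more after the last dose. Subjects who move to commercial or MAP drug are followed through ETT.

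SAP 10.3.1 classes as a post-treatment AE "any AE that worsened (either in severity or seriousness) or that was newly developed after the TE period". SAP 10.3 bases the AE analysis on events in the TE period, and protocol 12.3.4.1 restricts the AE summary tables to TEAEs.

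**The concern.** The analysis window and the collection window for the same subject can end on different dates, with the analysis window closing first. AEs that the protocol requires sites to collect within 28 days of the last dose then fall outside the primary safety tables.

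The group matters because early discontinuers include subjects who stop for an AE. A new serious or fatal event in the weeks after an early ETT would be missing from the serious-TEAE and fatal-TEAE counts, and from the numerators of any exposure-adjusted rates. Death shows the difficulty most clearly: a subject who has ETT and dies before the follow-up visit falls under no other completion rule in SAP 9.1.

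Information after ETT can be expected to exist. Protocol 9.10 keeps following subjects withdrawn from study drug who have not withdrawn consent, and asks sites to follow unresolved AEs.

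**Working it through.** The plan gives no figure to reproduce. The check is date logic.

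**Inputs.** Let d be the number of days from last dose to ETT, for a subject with no Safety Follow-up Visit who keeps consent and is not lost to follow-up.

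- TE end under SAP 9.1: min(28, d), because ETT is the only dated visit left in the rule.
- End of AE collection under protocol 13.1.1.3, general rule: 28 if d < 21; min(28, d) if d ≥ 21.
- End of AE collection on a move to commercial or MAP drug: d.
- Gap = end of AE collection − TE end.

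**General rule (no move to commercial or MAP drug)**

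| ETT day d | SAP TE end | Collection end | Gap (days) |
|---|---|---|---|
| 0 | 0 | 28 | 28 |
| 7 | 7 | 28 | 21 |
| 14 | 14 | 28 | 14 |
| 20 | 20 | 28 | 8 |
| 21 | 21 | 21 | 0 |
| 24 | 24 | 24 | 0 |
| 28 | 28 | 28 | 0 |

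For d from 0 to 20 the gap is 28 − d. As a share of the 28-day window it runs from 28/28 = 100% down to 8/28 = 29%.

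**Move to commercial or MAP drug.** Both documents use ETT, so the gap is d − d = 0 up to day 28. With ETT on day 35, collection runs 35 − 28 = 7 days past the TE period. That difference comes from the 28-day cap, not from the ETT rule.

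**Illustration (hypothetical subject).** ETT takes place on day 3, a new fatal event starts on day 15, and no follow-up visit occurs. The TE period ends on day 3 and collection runs to day 28. The event lies inside the collection window but is a post-treatment AE, so it is not counted among TEAEs leading to death.

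**After the fix.** Completion becomes the end of AE collection, still capped at day 28. The TE period then ends on day 28 for d = 0, 7, 14 and 20, on day 21 for d = 21, and on day 28 for d = 28. The gap is 0 in each case.

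**The case against.** The strongest reply is that the SAP has no settled rule here. The Safety Follow-up Visit was required, so it was applicable, and the SAP gives no date for a visit that was due but missed. One could argue that completion is then undefined and the 28-day limit applies. That reading is possible. However, the later of two dates, one of which never occurred, most naturally gives the other, and a programmer would probably code it so. The ambiguity is itself a reason to add the line.

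Other parts of the reply stand and limit the point:

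- **Scope.** A reader might infer that every early discontinuer without a follow-up visit is affected. Where the protocol itself drops the visit, collection also ends at ETT, or at day 28 if earlier under the general rule. Lost-to-follow-up subjects use the last contact date.
- **Size.** A reader might take the 7-day limit on ETT in protocol 9.1.3 and conclude that 21 to 28 days are always lost. That limit covers only discontinuation after regulatory refusal or lack of demonstrated benefit. For other early stops, including those for an AE, no day limit is given.
- **Asymmetry.** A reader might infer that only early stoppers have a short window. SAP 9.1 also ends participation at Week 96 for completers who enter Part B or move to commercial drug. Their last dose is the evening before (protocol 9.6), so their TE period ends about 1 day after it.
- **COVID-19.** A reader might expect many missed visits. The documents give no rate, and the addendum allows in-home visits, AE review by telephone and later unscheduled visits, all of which work against missed follow-up.
- **Consequence.** The events are not lost. Protocol 12.3.4.1 lists all AEs, and SAP 10.3.1.1 lists SAEs and all deaths with a TEAE flag. An on-treatment AE that led to stopping is already a TEAE; later worsening could change only its severity or seriousness category. But listings do not enter the incidence tables, and the flag would mark these events as not treatment-emergent.
- **No breach.** The protocol delegates the definition of completion and allows the TE period to end before day 28.

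**Conclusion.** The point holds for a defined, narrow group: early discontinuers who keep consent, have ETT less than 3 weeks after the last dose, do not have the required Safety Follow-up Visit, are not lost to follow-up and do not move to commercial or MAP drug. For them, 28 − d days of AE collection (28 days for ETT on day 0, 8 for day 20) fall outside the TE period, and events that begin or worsen in those days leave the TEAE summaries.

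This rests on reading the completion rule as falling back to ETT when the follow-up visit did not occur. The number of affected subjects is not given and may be small, so the effect on the tables cannot be sized. It is a mismatch between the SAP's analysis window and the protocol's AE collection window. It should be corrected because it touches the primary endpoint and the correction costs almost nothing.

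**What to change.** In SAP 9.1, split the completion rule for early discontinuers who have not withdrawn consent:

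1. If the Safety Follow-up Visit took place, keep the present rule.
2. If it did not, and ETT was 3 weeks or more after the last dose, or the subject moves to commercial or MAP drug, use the ETT date. The 28-day cap still applies.
3. Otherwise, use the end of AE collection in protocol 13.1.1.3: 28 days after the last dose, or the date of death, of later consent withdrawal or, if lost to follow-up, of last contact, if that is earlier.

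This also settles what the qualifier on the follow-up visit means when the visit was due but missed, and gives a completion date for a subject who dies after ETT. The cost is one SAP line and one change to the derivation of the TE end date. No visit, assessment or data collection changes.
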